12.5.1 Reporting a pause

If a pausing criterion is met, a description of the AE(s) or safety issue must be reported by the PI within 1 business day to the IRB.

12.5.2 Resumption of study vaccine after a pause

The PI will determine whether or not it is safe to resume administration of the study vaccine. The PI will notify the IRB of the decision on resumption of the study vaccine.

12.6 Halting Rules for the Protocol

Halting the study requires immediate discontinuation of all study vaccines for all subjects and suspension of enrollment until a decision is made whether or not to continue enrollment and study vaccine administration. Subjects continue to be followed by regularly scheduled protocol assessments during a halt.

The halting rule is:

- Any safety issue that the PI determines should halt the study.

The PI will determine if the study should be halted.

12.6.1 Reporting a halt

If a halting rule is met, a description of the AE(s) or safety issue must be reported by the PI within 1 business day to the IRB.

12.6.2 Resumption of a halted study

The PI will determine if it is safe to resume the study. The PI will notify the IRB of the decision on resumption of the study.

12.7 Study Discontinuation

The IRB, the NIAID, and other oversight bodies as applicable, as part of their duties to ensure that research subjects are protected, may discontinue the study at any time. Subsequent review of serious, unexpected, and related AEs by the IRB may also result in suspension of enrollment and further trial interventions/administration of study agent.

12.8 Premature Withdrawal of a Subject

An individual subject will be withdrawn for any of the following:

- An individual subject's decision. (The investigator should attempt to determine the reason for the subject's decision.)
- Non-compliance with study procedures to the extent that it is potentially harmful to the subject or to the integrity of the study data.
- One of the following changes in the subject's baseline condition after enrollment so that the subject no longer meets one or more eligibility criteria.
 - Unwilling to have samples and data stored for future research.
 - Develops a condition in the exclusion criteria that merits withdrawal per the opinion of the PI.
- The investigator determines that continued participation in the study would not be in the best interest of the subject.

12.9 Replacement of Withdrawn Subjects or Subjects Who Discontinue Study Treatment

Subjects who withdraw or are withdrawn from the study prior to day 14 of their first year of participation will be replaced. If a subject is replaced, all the data collected from that subject will still be included for the safety assessment.

13 Reporting Procedures

13.1 Reporting to the NIH IRB

UPs, non-compliance, and other reportable events will be reported to the NIH IRB according to HRPP Policy 801.

13.2 NIAID-specific Reporting

13.2.1 Reporting to the NIAID clinical director

The PI will report UPs, major protocol deviations, and deaths to the NIAID clinical director according to institutional timelines.

14 Clinical Monitoring Structure

To help ensure that NIH Office of Research Support and Compliance procedures and Good Clinical Practice (GCP) principles are being carried out, a Clinical Trials Management designee within the Office of Clinical Research Policy and Regulatory Operations, Regulatory Compliance and Human Subjects Protection Program will conduct a study initiation visit before study enrollment begins. The purpose of this meeting is to review with the PI and study team designees the roles and responsibilities concerning their commitment to adhere to the requirements of the protocol, especially in terms of the NIH Office of Human Subjects Research Protections reporting requirements for AEs, SAEs, and UPs. In addition, the quality management and data management plan for the study will be reviewed.

14.1 Quality Management Plan

During the study, the PI and study team will be responsible for implementing a quality management plan. Additionally, the study team will be responsible for completing and submitting a summary report on the quality plan to the NIAID clinical director or designee at least annually as detailed in the quality management plan. A courtesy copy will also be sent to Clinical Trials Management.

14.2 Safety Monitoring Plan

The data gathered during this study will be monitored by the PI for safety and compliance with protocol-specified requirements.

15 Statistical Considerations

This open-label, prospective, exploratory study will assess the baseline and post-vaccination immune responses of healthy volunteers to an approved seasonal influenza vaccine. Subjects will undergo blood collections on days -7 and 0 before vaccination as well as regularly after vaccination. Blood samples will be used to assess short- and long-term immunological effects of immunization, including assessment of antibody titer response to vaccination. Subjects may optionally continue study participation annually through multiple influenza seasons.

15.1 Study Objectives

The primary objective of this study is to identify baseline correlates of immune response to the seasonal influenza vaccine in healthy individuals. The secondary objective is to validate the findings of prior study 09-H-0239, specifically the relationship between cell populations and/or gene transcripts at baseline and after vaccination that correlate with vaccine immune response. Exploratory objectives include examining pre- to post-vaccination changes in multiple biomarkers, correlating changes in biomarkers, identifying networks of biomarkers that act in concert, and assessing changes in biomarkers and biomarker relationships over time and over seasons.

15.2 Sample Size Justification

This is a hypothesis-generating study designed to examine relationships between different biomarkers measured at baseline and post-vaccination immune responses. To set the sample size, we used data from a previous study designed to examine biomarkers (09-H-0239).³ That study identified a significant relationship between $Y = \text{adjMFC}$ (a measure of vaccine-induced immune response adjusted for baseline response) and $X = \text{ID96_0}$ (a baseline readout of the frequency a $\text{CD38}^+ \text{CD20}^+$ memory B cell population). The estimated slope was 0.29 with an estimated standard error of $0.12 = \sqrt{\text{var}(R)/((n-1)*\text{var}(X))}$, where $\text{var}(R) = 2.09$ is the sample variance of the residuals from the regression line, $\text{var}(X) = 3.03$ is the sample variance of X , and $n = 49$ is the sample size of that study.

We used these estimates as a reference to set the sample size for the current study with the objective to identify a *new* biomarker that correlates with adjMFC with a similar or stronger relationship than was observed in 09-H-0239. We assumed the same error variance of $\text{var}(R) = 2.09$ and the same sample variance of $\text{var}(X) = 3.03$, and we assumed that the true slope is 0.29. We determined the power by using the Wald test where the slope is zero (i.e., the Wald test is $B/\text{se}(B)$ where B is the estimated slope and $\text{se}(B)$ is the estimated standard error). We assumed that this test is approximately standard normal under the null and approximately normal with mean $0.29/\sqrt{\text{var}(R)/((n-1)*\text{var}(X))}$ and variance 1 under the alternative.

We plan to correlate adjMFC with separate distinct collections of biomarkers (e.g., immune phenotyping as measured by flow cytometry or CyTOF, or RNA-seq). For each distinct collection, a multiplicity adjustment would be performed. Power calculations were performed (Table 2) considering various sample sizes, allowing for 5% missing data, and using a two-sided test with an alpha of 0.05 and with an illustrative Bonferroni adjustment for a moderate collection of biomarkers (50; e.g., nontrivial peripheral blood cell subsets measured by flow cytometry or CyTOF). With a sample size of 170 and 10% missing data, we have more than 80% power to identify biomarkers that have true slopes of 0.29 or better even with adjustment for 50 multiple comparisons.

Table 2. Power to detect an association between a baseline biomarker and adjMFC under different sample sizes and multiplicity corrections.

Sample Size	Effective Sample Size (10% missing data)	Power with Adjustment for 50 Comparisons
120	108	.63
170	153	.85
230	207	.96

Sample Size	Effective Sample Size (10% missing data)	Power with Adjustment for 50 Comparisons
280	252	.99

Subjects will have the option to participate for multiple years. Generalized estimating equations (GEE) analyses that use all available measurements from each subject with proper correction for within subject correlation will have greater power than those described in Table 2. Analyses will be stratified by year by including a separate term for each cohort year in the GEE models. Such stratification has a negligible effect on power calculations.

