15.3 Description of the Analyses

The primary analysis will be to correlate multiple baseline biomarkers with the vaccine-induced outcome adjMFC using GEE to reflect clustering at the subject level due to multiple measurements over multiple years. Analyses will be stratified by year by including a separate term for each cohort year in the GEE models. Two-sided testing will be performed with an adjustment for multiplicity such as the Bonferroni to control the overall type I error rate at 0.05.

For the first secondary analysis, a similar analysis strategy will be used as in the primary analysis, but the relationship between the vaccine-induced outcome adjMFC and baseline biomarkers (specifically ID_96 [CD38⁺ CD20⁺ B cell frequencies and/or transcriptomic signatures]) and post-vaccination biomarkers (specifically ID_87 [plasmablast cell frequencies and/or transcriptomic signatures]) will be examined separately. Specifically, we will evaluate 1) whether the slope between adjMFC and ID96_0 (measured at day 0) is zero using GEE, as described for the primary analysis with no adjustment for multiplicity, and 2) whether the slope between adjMFC and ID_87, measured at day 7/day 0) is zero using GEE, as described for the primary analysis with no adjustment for multiplicity. Both analyses are designed to replicate findings from 09-H-0239.³

Analysis of the secondary endpoint on SARS-CoV-2 will involve comparing the results of the above analyses by cohort: 1) those subjects with prior symptomatic SARS-CoV-2 infection, 2) those subjects with prior asymptomatic SARS-CoV-2 infection, and 3) those subjects without a history of SARS-CoV-2 infection.

The exploratory analyses will involve both unsupervised and supervised analyses using the framework developed in 09-H-0239. In addition to that framework, under this protocol we will be able to characterize immune responses and biomarker relationships over multiple seasons in the same individual. The first general aim is to perform unsupervised analysis of the immune states of the baseline along the measured phenotypic dimensions, including PBMC/cell subset

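### The primary GEE regresses a baseline-adjusted outcome (adjMFC) on markers not adjusted for the day 0 titer, which costs power for titer-related markers; a day 0 titer covariate would recover it

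*Combined protocol and SAP*

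**What the plan says.** Section 15.2 defines the outcome only in words: adjMFC is "a measure of vaccine-induced immune response adjusted for baseline response". Neither the method of adjustment nor the way strains are combined is given.

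Section 15.3 states: "The primary analysis will be to correlate multiple baseline biomarkers with the vaccine-induced outcome adjMFC using GEE". The only other term named for the model is cohort year: "Analyses will be stratified by year by including a separate term for each cohort year in the GEE models". The first secondary analysis uses the same model for ID96_0 at day 0 and for ID_87 (day 7 relative to day 0), without multiplicity adjustment, in order to replicate 09-H-0239. Nowhere is the day 0 titer entered in the GEE, and nowhere are the biomarkers adjusted for it.

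For sample size, Section 15.2 takes the slope of adjMFC on ID96_0 from 09-H-0239 and carries it forward: "we assumed that the true slope is 0.29". The test is described as "using a two-sided test with an alpha of 0.05 and with an illustrative Bonferroni adjustment for a moderate collection of biomarkers (50" tests), and the conclusion is: "With a sample size of 170 and 10% missing data, we have more than 80% power". Table 2 gives 0.85 for N = 170, effective n = 153.

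**The concern.** Suppose the day 0 titer has been regressed out of the response and the result is then regressed on an unadjusted marker. The part of the marker that moves with the titer cannot explain anything in such an outcome, yet it still counts as marker variance. The slope falls, and the standard error is computed as if all of the marker's variance were usable. The test statistic is then too small even when there is no association, so the test rejects less often than its nominal level.

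The primary objective is to find baseline correlates under a strict per-test threshold. The loss would fall selectively on markers related to existing influenza immunity, which Section 2.3 names as an interest. Such markers could be ranked too low or missed.

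**Working it through.** **Inputs.** From Section 15.2: slope b = 0.29, var(R) = 2.09, var(X) = 3.03, two-sided 0.05 over 50 tests = 0.001, so the critical value is c = 3.2905. From Table 2: n = 153. Assumed: R2, and that adjMFC is a linear residual on the day 0 titer in the same data.

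**The plan's own figures.** The prior study's standard error is sqrt(2.09/(48 × 3.03)) = 0.120, against 0.12 stated. For n = 153 the standard error is sqrt(2.09/(152 × 3.03)) = 0.0674, the mean of the Wald statistic is 0.29/0.0674 = 4.305, and power is Phi(4.305 - 3.2905) = 0.845, against 0.85 stated. The other rows also reproduce (0.626, 0.957 and 0.988 against 0.63, 0.96 and 0.99). One sentence of Section 15.2 mentions 5% missing data; the table reproduces with 10%, which is used here.

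**Planned model against the model with the titer.** Both slopes share one numerator, the covariance of the marker with the titer-adjusted response. The planned model divides it by var(X); the model with the titer divides it by var(X)(1 - R2). Hence:

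- planned slope = (1 - R2) × slope at a fixed titer;
- planned z ≈ sqrt(1 - R2) × z from the model with the titer.

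**Null behaviour.** A true slope of zero is zero in both models, but the planned z then has variance of about 1 - R2. At nominal 5% it rejects with probability 2[1 - Phi(1.96/sqrt(1 - R2))], which is 3.9%, 2.8% and 1.9% at R2 = 0.1, 0.2 and 0.3. Simulation gave 3.8%, 3.0% and 2.4%. The model with the titer stays at about 5%.

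**Power when 0.29 is the slope on adjMFC, as in Section 15.2.**

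- Planned: Phi((4.305 - 3.2905)/sqrt(1 - R2)).
- With titer: Phi(4.305/sqrt(1 - R2) - 3.2905).

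| R2 | Formula: planned | Formula: with titer | Simulated: planned | Simulated: with titer | Slope at fixed titer, 0.29/(1 - R2) |
|---|---|---|---|---|---|
| 0 | 0.845 | 0.845 | equal | equal | 0.290 |
| 0.04 | 0.850 | 0.865 | about 2 points below | about 2 points above | 0.302 |
| 0.1 | 0.858 | 0.894 | 0.84 | 0.88 | 0.322 |
| 0.2 | 0.872 | 0.936 | 0.85 | 0.93 | 0.362 |
| 0.3 | 0.887 | 0.968 | 0.87 | 0.97 | 0.414 |

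In the R2 = 0.04 row the simulated columns mean that the two models differ by about 2 points. The simulation used n = 153, one record per subject, and held the planned model's residual variance at 2.09. It runs one to two points below the normal formula; the gap between models is much the same.

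**If the adjustment is not linear.** This was checked with adjMFC built by removing titer-quintile means, at a correlation of 0.5 (R2 = 0.25). Here 0.29 was set as the slope at a fixed titer, so the powers are not comparable with the table. Adding a linear titer term moved the slope from 0.196 to 0.284 and power from 0.33 to 0.64. Most of the loss is recovered, but not exactly all of it.

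**The case against.** Two stronger conclusions are tempting, and the documents support neither.

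*That Table 2 overstates power.* If 0.29 were the slope at a fixed titer, planned power would fall to 0.71, 0.55 and 0.38 at R2 = 0.1, 0.2 and 0.3. But Section 15.2 gives 0.29 as the slope of adjMFC itself on ID96_0, with a single-predictor standard error that reproduces. Whatever shrinkage exists is already in 0.29. On that scale the claim of more than 80% power holds at every R2 tried.

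*That the replication of 0.29 is biased toward zero.* The replication regresses the same outcome on the same marker, so it is like for like provided adjMFC is built as before. Adding the titer there would create the mismatch: at R2 = 0.2 the target would move to 0.29/0.8 = 0.3625.

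Three further points stand as limits. The residual construction is an inference from a short verbal description, and the strain summary that the covariate should match is undefined. The documents give no correlation between any marker and the day 0 titer, and the gain is small when that correlation is weak. The planned test is valid, since it errs on the conservative side, and the study calls itself hypothesis-generating. The Lasso and other multiple-regression analyses in Section 15.3 could include the titer, but they are exploratory and do not name it.

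None of this removes the efficiency loss in the primary test.

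**Conclusion.** The point holds as a loss of efficiency in the primary discovery analysis. It is not an error in Table 2, a bias in the replication, or an invalid test. Relative to a model containing the day 0 titer, the planned test gives up about 4 points of power at R2 = 0.1, 8 at R2 = 0.2 and 10 at R2 = 0.3. It gives up nothing at R2 = 0 and about 2 points at R2 = 0.04.

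This rests on three assumptions: adjMFC is a residual on the day 0 titer, the marker is correlated with that titer to the stated degree, and one record per subject represents the GEE well enough. Because R2 is unknown, the size is a range. The change is worth making because the covariate is already collected and costs almost nothing if R2 proves to be zero.

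**What to change.** In Section 15.3:

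1. State how adjMFC is constructed, including the scale, the strain summary and the form of the baseline adjustment.
2. Add the log day 0 microneutralization titer, in the scale and strain summary used to build adjMFC, as a covariate in the primary GEE beside the cohort-year terms. With a linear adjustment this does not adjust twice: it returns the slope at a fixed day 0 titer.
3. Keep the replication GEEs for ID96_0 and ID_87 as planned, for comparability with 09-H-0239, and report the titer-adjusted slope beside each as a supplement.

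The cost is a few sentences and one degree of freedom; the day 0 titer is already half of the primary endpoint. The primary slope would then be read at a fixed day 0 titer and would no longer be directly comparable with 0.29, which the text should say.

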7.2 Laboratory Evaluations

Pre- and post-vaccination whole blood samples will be processed to isolate serum, PBMCs, RNA, and TBNK cells, which will be used for the following research evaluations:

- Antibody titers on serum.
- CBC with differential.
- Lymphocyte phenotyping (TBNK flow cytometry performed by the NIH CC).
- Whole blood transcriptome as analyzed by RNA-seq from stabilized RNA (e.g., via Tempus or PAXgene tubes).

Additional research evaluations to evaluate a large number of parameters may include but are not limited to the following:

- Flow cytometry on whole blood and/or immune cell subsets.
- Cellular transcriptional activity in immune cell subsets as analyzed by RNA-seq and/or microarrays.
- Quantification of gene expression (transcriptome) of PBMCs with RNA-seq and/or microarrays.
- Characterization of chromatin accessibility and promoter/enhancer landscapes in immune cell subsets with ATAC-seq and/or other techniques.
- Targeted genetic analyses including genotyping of specific regions of the genome (e.g., human leukocyte antigen and single nucleotide polymorphism typing), if not already performed on another protocol.
- Measurement of relative abundance of serum proteins with SomaLogic's SOMAscan assay or other assays.
- Serum antibody titers.
- Serum SARS-CoV-2 antibody testing using the Roche Elecsys[®] Anti-SARS-CoV-2 antibody test (under Emergency Use Authorization), which is classified as a Non-Significant Risk device because it does not meet any of the following definitions of a Significant Risk Device under 21 CFR 812.3(m):
 - Is intended as an implant and presents a potential for serious risk to the health, safety, or welfare of a subject;
 - Is purported or represented to be for use supporting or sustaining human life and presents a potential for serious risk to the health, safety, or welfare of a subject;
 - Is for a use of substantial importance in diagnosing, curing, mitigating, or treating disease, or otherwise preventing impairment of human health and presents a potential for serious risk to the health, safety, or welfare of a subject; or
 - Otherwise presents a potential for serious risk to the health, safety, or welfare of a subject.

The use of the Roche Elecsys[®] Anti-SARS-CoV-2 antibody test as a Non-Significant Risk device will follow the abbreviated requirements under 21 CFR 812.2(b)(1).

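### Section 15.2 shows power for 50 comparisons only: its 80% claim holds up to 93 comparisons per collection and does not extend to gene-level RNA-seq

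*Combined protocol and SAP*

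**What the plan says.** Section 15.2 plans to correlate adjMFC with several separate collections of biomarkers. It gives cytometry phenotyping and RNA-seq as examples, and each collection gets its own multiplicity adjustment. The power calculation takes its effect from one marker in the earlier study, a CD38+ CD20+ memory B-cell frequency: "we assumed that the true slope is 0.29", with the residual and marker variances also carried over. The test is specified too: "We determined the power by using the Wald test where the slope is zero". The multiplicity case is an "illustrative Bonferroni adjustment for a moderate collection of biomarkers (50; e.g., nontrivial peripheral blood cell subsets measured by flow cytometry or CyTOF"). The text then claims more than 80% power at 170 subjects with 10% missing, for 50 comparisons. The title of Table 2 refers to different multiplicity corrections, but the table has a single correction column, for 50.

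Section 15.3 makes the correlation of baseline biomarkers with adjMFC the primary analysis, with an "adjustment for multiplicity such as the Bonferroni to control the overall type I error rate at 0.05".

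Section 7.2 lists "Whole blood transcriptome as analyzed by RNA-seq from stabilized RNA" among the evaluations for which samples will be used. Research flow cytometry comes under a second list, introduced by "Additional research evaluations to evaluate a large number of parameters may include but are not limited to the following".

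**The concern.** The sample size is justified on a collection of 50 cell subsets. RNA-seq belongs to the same primary analysis, and a transcriptome tested gene by gene is a far larger family. The only adjustment named, and the only one powered, is Bonferroni, whose cut-off rises with the number of tests and takes no account of correlation between markers. If the RNA-seq collection is large, the power in Table 2 does not describe it. A null RNA-seq result would then be hard to interpret, because the plan gives neither the number of tests nor the chance of detecting the planned effect.

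**Working it through.** **Inputs, all from 15.2 and Table 2:** slope 0.29; var(R) = 2.09; var(X) = 3.03; two-sided alpha 0.05; effective n = 170 × 0.90 = 153; normal approximation with variance 1.

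**Formula.** With m Bonferroni comparisons, power = Phi(mu − z(1 − 0.025/m)), where mu = 0.29 / sqrt(2.09 / ((n − 1) × 3.03)).

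At n = 153 the standard error is sqrt(2.09 / (152 × 3.03)) = 0.0674, so mu = 4.305.

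**Reproducing the plan.** At m = 50 the cut-off is 3.291, and Phi(4.305 − 3.291) = .845, which the plan states as .85. The other rows of Table 2 also reproduce: .626 at n = 108 (stated .63), .957 at 207 (.96) and .988 at 252 (.99). The earlier study's standard error comes out at sqrt(2.09 / (48 × 3.03)) = 0.120, as stated.

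**Changing only m, at n = 153:**

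| Comparisons m | Cut-off | Power |
|---|---|---|
| 50 | 3.291 | .845 |
| 93 | 3.461 | .801 |
| 94 | 3.464 | .7998 |
| 100 | 3.481 | .795 |
| 1,000 | 4.056 | .598 |
| 10,000 | 4.565 | .397 |
| 20,000 | 4.708 | .343 |

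The 80% claim therefore holds up to 93 comparisons. Power reaches .50 where the cut-off equals mu, at about 2,990 comparisons. The values of m from 1,000 to 20,000 are assumptions.

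**Missing-data rate.** The text of 15.2 also mentions 5% missing, while Table 2 uses 10%. With 5% missing (n = 161.5), power is .871 at 50 tests, .444 at 10,000 and .388 at 20,000, and the 80% limit moves to 146 comparisons.

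**What maxT would gain.** Assume m markers in k independent blocks of b, with correlation r within a block. The maxT cut-off c solves P(block maximum of |Z| ≤ c)^k = 0.95. Power is then Phi(4.305 − c), using the single-step cut-off; step-down can only lower it.

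| m | Block size b | r = .5 | r = .7 | r = .9 | Bonferroni |
|---|---|---|---|---|---|
| 50 | 5 | .852 | .862 | .887 | .845 |
| 50 | 10 | .856 | .873 | .909 | .845 |
| 10,000 | 5 | .401 | .406 | .435 | .397 |
| 10,000 | 10 | .402 | .412 | .458 | .397 |

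For 50 markers the gain is about 1 to 6 points. For 10,000 it is under 1 point at r = .5 and about 4 to 6 points at r = .9. Holm adds almost nothing here: at 10,000 tests, even after 100 earlier rejections, power is .398 against .397.

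**The case against.** The strongest reply is that 15.2 promises nothing for RNA-seq. It calls the 50-test case illustrative and the collection moderate, and it limits the 80% statement to 50 comparisons, which the design delivers. That stands: the stated figure is not wrong. The gap is that another named primary collection has no test count and no power.

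Four stronger readings are tempting, and the documents do not support them.

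- **The primary analysis will more often miss than find a transcript with the planned effect.** This is true only above about 2,990 tests. At 1,000 tests power is .60. The documents give no transcript count and do not say that the primary RNA-seq collection is tested gene by gene. Signatures appear in the secondary analysis, and genes and gene modules in the exploratory one.
- **Bonferroni is a binding rule.** Section 15.3 offers it as an example, so Holm and maxT are already allowed.
- **RNA-seq is the guaranteed data source and cytometry the optional one.** Section 7.2 taken alone reads that way. The Protocol Summary, the Précis and 3.2.3 all list whole-blood RNA-seq among evaluations that may be done.
- **Gene modules must replace single genes as the primary RNA-seq collection.** That is a scientific choice in a study that describes itself as hypothesis-generating.

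Two further limits stand. The effect size comes from a B-cell frequency (correlation 0.29 × sqrt(3.03) / sqrt(0.29² × 3.03 + 2.09) = .33), and 15.2 aims at a similar or stronger relationship. At 10,000 tests, 80% power would need a slope of about (4.565 + 0.842) × 0.0674 = 0.364, with the variances held. Also, 15.2 says that repeat-season GEE data will give more power than Table 2. Repeat participation is optional and no size is given for that gain, so it cannot be counted here.

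**Conclusion.** The concern holds as an incomplete power statement and an adjustment that can be improved, not as an error in Table 2. The .85 is right for 50 comparisons at n = 153, and the 80% claim runs out after 93 comparisons per collection. For gene-level RNA-seq with Bonferroni, power for the planned effect would be about .60 to .34.

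That range rests on three assumptions: 1,000 to 20,000 tests, the cell-frequency slope and variance applying to transcripts, and no gain from repeat seasons. It also takes the adjustment within each collection, as 15.2 says. The overall control in 15.3, if it meant across collections, would lower power further.

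The maxT gain depends on assumed correlation blocks. It is modest for 50 markers, and it does not bring a gene-level collection of 10,000 near 80%. The gene-level shortfall therefore has to be stated openly, because a change of method will not remove it.

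**What to change.** 1. In 15.3, replace the open-ended reference to Bonferroni with step-down maxT within each collection at the same 0.05. Resample whole subjects, so that a subject's repeat seasons stay together. Name Holm as the fallback; it never does worse than Bonferroni.
2. In 15.2, state that the 80% claim holds up to 93 comparisons per collection at 10% missing, and that it does not extend to gene-level RNA-seq.
3. Add a large-collection column to Table 2, with its number of tests labelled as an assumption. For example, 10,000 tests give .40 at 170 enrolled under Bonferroni.

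The cost is SAP wording, modest computing, and a lower stated power for large collections. No extra subjects are needed.

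The investigators may also choose to make a fixed list of gene-module scores the primary RNA-seq collection. Fifty or fewer scores would give at least .845 for a module that carries the planned effect, which the documents do not establish. Single-gene results would then become exploratory. This is an option, not a required correction.
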